5.7.3. Additional Safety Assessments

5.7.3.1. Clinical Laboratory Tests

Clinical laboratory tests will be displayed for the participants included in the safety analysis set.

Descriptive statistics will be presented for selected chemistry, hematology, and urinalysis (pH and specific gravity) laboratory tests at scheduled time points.

Change from baseline over time through Week 52 will be summarized for selected chemistry, hematology, and urinalysis (pH, and specific gravity) tests and displayed by intervention group. A box plot of change from baseline over time through Week 52 will be provided for the following laboratory tests: hematology: hemoglobin, platelets, total WBC, absolute lymphocytes, and absolute neutrophils; chemistry: ALT, AST, Alkaline phosphatase and total bilirubin.

Applicable lab results are to be graded based on National Cancer Institute Common Terminology Criteria for Adverse Events (NCI-CTCAE) version 5.0. The laboratory tests not included in the NCI-CTCAE criteria will not be presented in the corresponding tables or listings.

Summary of maximum postbaseline NCI-CTCAE toxicity grade through Week 52 will be presented. Additionally, shift table from baseline laboratory value to the worst toxicity grade through Week 52 in chemistry and hematology tests with NCI-CTCAE will be summarized for the following lab parameters: hematology: hemoglobin, platelets, total WBC, absolute lymphocytes, and absolute neutrophils; chemistry: ALT, AST, Alkaline phosphatase and total bilirubin.

Proportion of participants with maximum postbaseline ALT and AST through Week 52 will be provided for the categories:

- >1 to ≤ 3 x ULN
- >3 to ≤ 5 x ULN
- >5 to ≤ 10 x ULN
- >10 to ≤ 20 x ULN
- >20 x ULN

Besides, proportion of participants with total bilirubin >2 x ULN and either AST or ALT ≥ 3 x ULN at the same timepoint will also be provided.

In addition, proportion of participants with maximum postbaseline alkaline phosphatase through Week 52 will be provided for the categories:

- ≤ 1 x ULN
- >1 to ≤ 1.5 x ULN
- >1.5 to ≤ 2.5 x ULN
- >2.5 to ≤ 5 x ULN
- >5 to ≤ 20 x ULN
- >20 x ULN

Above analysis will also be summarized through LTE period.

Listings of participants with any abnormal postbaseline laboratory values of NCI-CTCAE grade ≥ 2 or any abnormal postbaseline laboratory values of reference range will also be provided.

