6.10. Appendix 10 Laboratory Toxicity Grading

The grading scale use for lab assessments is based on ‘Common Terminology Criteria for Adverse Events (CTCAE) v5.0’.

If a laboratory value falls within the grading as specified below but also within the local laboratory normal limits, the value is considered to be normal and will be reset to grade 0.

Prebaseline measurements will use the same grading ranges as applied to baseline measurements. In case a test has two sets of ranges – one for baseline normal and one for baseline abnormal, the one for baseline normal will be applied for all measurements taken prebaseline and on baseline.

Text in gray italic in the table is present in the grading scale, but is not applied by Janssen when grading lab data.

CTCAE Term	Grade 1	Grade 2	Grade 3	Grade 4	Janssen implementation notes
Blood and lymphatic system disorders					
Anemia	Hemoglobin (Hgb) <LLN - 10.0 g/dL; <LLN - 6.2 mmol/L; <LLN - 100 g/L	Hemoglobin (Hgb) <10.0 - 8.0 g/dL; <6.2 - 4.9 mmol/L; <100 - 80g/L	Hemoglobin (Hgb) <8.0 g/dL; <4.9 mmol/L; <80 g/L; transfusion indicated	Life-threatening consequences; urgent intervention indicated	Clinical signs and symptoms are not taken into consideration for grading.
Leukocytosis	-	-	>100,000/mm ³ ; >100 x 10 ⁹ /L	Clinical manifestations of leucostasis; urgent intervention indicated	Clinical signs and symptoms are not taken into consideration for grading; Added ranges in SI unit (x 10 ⁹ /L)
Investigations					
Activated partial thromboplastin time prolonged	>ULN - 1.5 x ULN	>1.5 - 2.5 x ULN	>2.5 x ULN; bleeding	-	Clinical signs and symptoms are not taken into consideration for grading.
Alanine aminotransferase increased	>ULN - 3.0 x ULN if baseline was normal; 1.5 - 3.0 x baseline if baseline was abnormal	>3.0 - 5.0 x ULN if baseline was normal; >3.0 - 5.0 x baseline if baseline was abnormal	>5.0 - 20.0 x ULN if baseline was normal; >5.0 - 20.0 x baseline if baseline was abnormal	>20.0 x ULN if baseline was normal; >20.0 x baseline if baseline was abnormal	Ranges defined for “abnormal baseline” are applied only if baseline > ULN. If baseline < LLN, then ranges for “normal baseline” are applied.

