Alkaline phosphatase increased	>ULN - 2.5 x ULN if baseline was normal; 2.0 - 2.5 x baseline if baseline was abnormal	>2.5 - 5.0 x ULN if baseline was normal; >2.5 - 5.0 x baseline if baseline was abnormal	>5.0 - 20.0 x ULN if baseline was normal; >5.0 - 20.0 x baseline if baseline was abnormal	>20.0 x ULN if baseline was normal; >20.0 x baseline if baseline was abnormal	Ranges defined for “abnormal baseline” are applied only if baseline > ULN. If baseline < LLN, then ranges for “normal baseline” are applied.
Aspartate aminotransferase increased	>ULN - 3.0 x ULN if baseline was normal; 1.5 - 3.0 x baseline if baseline was abnormal	>3.0 - 5.0 x ULN if baseline was normal; >3.0 - 5.0 x baseline if baseline was abnormal	>5.0 - 20.0 x ULN if baseline was normal; >5.0 - 20.0 x baseline if baseline was abnormal	>20.0 x ULN if baseline was normal; >20.0 x baseline if baseline was abnormal	Ranges defined for “abnormal baseline” are applied only if baseline > ULN. If baseline < LLN, then ranges for

CTCAE Term	Grade 1	Grade 2	Grade 3	Grade 4	Janssen implementation notes
					“normal baseline” are applied.
Blood bilirubin increased	>ULN - 1.5 x ULN if baseline was normal; > 1.0 - 1.5 x baseline if baseline was abnormal	>1.5 - 3.0 x ULN if baseline was normal; >1.5 - 3.0 x baseline if baseline was abnormal	>3.0 - 10.0 x ULN if baseline was normal; >3.0 - 10.0 x baseline if baseline was abnormal	>10.0 x ULN if baseline was normal; >10.0 x baseline if baseline was abnormal	Ranges defined for “abnormal baseline” are applied only if baseline > ULN. If baseline < LLN, then ranges for “normal baseline” are applied.
CD4 lymphocytes decreased	<LLN - 500/mm ³ ; <LLN - 0.5 x 10 ⁹ /L	<500 - 200/mm ³ ; <0.5 - 0.2 x 10 ⁹ /L	<200 - 50/mm ³ ; <0.2 x 0.05 - 10 ⁹ /L	<50/mm ³ ; <0.05 x 10 ⁹ /L	
Cholesterol high	>ULN - 300 mg/dL; >ULN - 7.75 mmol/L	>300 - 400 mg/dL; >7.75 - 10.34 mmol/L	>400 - 500 mg/dL; >10.34 - 12.92 mmol/L	>500 mg/dL; >12.92 mmol/L	
CPK increased	>ULN - 2.5 x ULN	>2.5 x ULN - 5 x ULN	>5 x ULN - 10 x ULN	>10 x ULN	
Creatinine increased	Creatine Kinase >ULN - 1.5 x ULN	Creatine Kinase >1.5 - 3.0 x baseline; >1.5 - 3.0 x ULN	Creatine Kinase >3.0 x baseline; >3.0 - 6.0 x ULN	Creatine Kinase >6.0 x ULN	

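### SAP Appendix 10 names creatine kinase in all four grade cells of its creatinine row, leaving serum creatinine without limits of its own; separately, the SI unit of the haemoglobin entry limit is wrong (minor)

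*SAP*

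**What the plan says.** **Grading table (SAP 6.10, Appendix 10).** The row whose CTCAE term is *Creatinine increased* has these four cells:

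- Grade 1: "Creatine Kinase >ULN - 1.5 x ULN"
- Grade 2: "Creatine Kinase >1.5 - 3.0 x baseline; >1.5 - 3.0 x ULN"
- Grade 3: "Creatine Kinase >3.0 x baseline; >3.0 - 6.0 x ULN"
- Grade 4: "Creatine Kinase >6.0 x ULN"

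Its implementation-notes cell is empty. The row directly above, "CPK increased", grades the same enzyme on another scale; its Grade 2 cell is ">2.5 x ULN - 5 x ULN". No other row gives limits for serum creatinine. A footnote to the table assigns Grade 0 where a test is described in the table but the value earns no grade of 1 or higher.

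**Use of the table (SAP 5.7.3.1).** Results are graded on NCI-CTCAE version 5.0. The grades feed a summary of the maximum post-baseline grade and a listing of participants with grade 2 or higher values or with values outside the reference range. The section adds: "The laboratory tests not included in the NCI-CTCAE criteria will not be presented in the corresponding tables or listings".

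**Chemistry panel (protocol 10.2, Appendix 2).** Creatinine and creatine phosphokinase are separate scheduled tests.

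**Haemoglobin.** Protocol 5.1, criterion 12.1a, sets a minimum of 9 g/dL and gives the SI equivalent as 90 mmol/L. The anemia row of SAP Appendix 10 gives its Grade 2 range in two SI units, "<6.2 - 4.9 mmol/L; <100 - 80g/L", next to 10.0 to 8.0 g/dL.

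**The concern.** Creatinine and creatine kinase are different analytes: one reflects renal function, the other is a muscle enzyme. The wrong name occurs four times, each time with complete limits, so it does not look like a text-extraction fault. A grading table exists so that the programmer need not guess. Here the label points to one analyte, the cells point to another, and the second analyte already has its own row.

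What is at stake is how laboratory toxicity is reported. Under the literal text a raised creatinine would carry no grade or would be shown as Grade 0, and CK could be graded on either of two scales.

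The haemoglobin entry is a separate unit error in an eligibility criterion. The two figures offered as equivalent are not equivalent.

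**Working it through.** **1. Which analyte each row grades.** All inputs are from SAP Appendix 10.

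| Row label | Analyte in the cells | Upper limits of Grades 1 / 2 / 3 (x ULN) |
|---|---|---|
| CPK increased | CPK | 2.5 / 5 / 10 |
| Creatinine increased | Creatine kinase, four times | 1.5 / 3 / 6 |

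Taken at its word, the table has two scales for CK and none for creatinine.

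**2. Size of the CK conflict.** This uses the ULN limits and assumes a baseline CK at ULN, so that the x-baseline and x-ULN limits of the creatinine row coincide.

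| CK (x ULN) | Grade, CPK row | Grade, creatinine row |
|---|---|---|
| 1.2 | 1 | 1 |
| 2 | 1 | 2 |
| 3 | 2 | 2 |
| 4 | 2 | 3 |
| 6 | 3 | 3 |
| 7 | 3 | 4 |
| 12 | 4 | 4 |

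The rows disagree by one grade for CK above 1.5 up to 2.5, above 3 up to 5, and above 6 up to 10 x ULN. They agree elsewhere. With a baseline below ULN the gap can widen. As an illustration, if baseline is 0.5 x ULN, a CK of 2 x ULN is 2 / 0.5 = 4 x baseline. That is Grade 3 on the x-baseline limit of the creatinine row and Grade 1 in the CPK row.

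**3. What happens to creatinine on a literal reading.** If the row is taken to describe CK only, creatinine has no criteria in the table and is ungraded. If the label is enough for creatinine to count as described in the table, no cell supplies a limit it can exceed, and the footnote makes it Grade 0 at any value.

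**4. Which outputs are exposed.** In SAP 5.7.3.1 the maximum-grade summary and the grade 2 or higher part of the listing depend on these cells. The shift tables and box plots name haemoglobin, platelets, white cells, lymphocytes, neutrophils, ALT, AST, alkaline phosphatase and total bilirubin, so neither creatinine nor CK is among them. The reference-range part of the listing needs no grade.

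**5. Haemoglobin conversion.** The SAP anemia row equates 10.0 g/dL, 6.2 mmol/L and 100 g/L, and equates 8.0 g/dL, 4.9 mmol/L and 80 g/L.

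- g/L per g/dL: 100 / 10.0 = 80 / 8.0 = 10, so 9 g/dL = 90 g/L.
- mmol/L per g/dL: 6.2 / 10.0 = 0.62, so 9 g/dL = 9 x 0.62 = 5.58 mmol/L. If both pairs are treated as rounded to one decimal, the factor lies between 6.15 / 10 = 0.615 and 4.95 / 8 = 0.619, which gives 5.54 to 5.57 mmol/L.
- Ratio of the printed SI figure to the converted limit: 90 / 5.58 = 16.1.
- Converting back: 90 / 0.619 to 90 / 0.615, or about 145 to 146 g/dL.

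The plan's 90 mmol/L is therefore not reproduced from 9 g/dL. The number 90 is reproduced only with the unit g/L.

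**The case against.** The best defence is that the intent is easy to see. The CTCAE term still says creatinine, SAP 5.7.3.1 bases grading on NCI-CTCAE version 5.0, and CK has its own row immediately above. A programmer may well apply the 1.5 / 3 / 6 limits to creatinine without noticing the slip. That is fair. It is why the defect is an ambiguity with a wrong literal reading, and not proof that results will be misreported.

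Four stronger readings are tempting, and the documents do not support them.

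- *Creatinine would drop out of the laboratory outputs.* The omission rule turns on whether a test is in the NCI-CTCAE criteria, not on the wording of one cell, and the appendix lists creatinine as a CTCAE term. An out-of-range creatinine also reaches the listing through its reference-range part.
- *CK toxicity will be inflated.* That requires grading CK from a row labelled creatinine in preference to the CPK row.
- *Renal crisis would be missed, or an endpoint affected.* Step 1 of ACR CRISS is judged by investigators (protocol 8.1.2, SAP 5.4.2.1). Renal eligibility rests on its own criteria in protocol 5.1 and 5.2. Neither uses Appendix 10 grades.
- *No one could be enrolled.* The 9 g/dL limit stands beside the SI figure. Haematology is run by the central laboratory (protocol 10.2), and the SAP works with central-laboratory haemoglobin in g/dL (5.4.2.1). A limit that nobody could meet would be noticed at once.

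What the defence does not remove is that both texts are wrong as printed, and both are operative rules.

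**Conclusion.** The point holds as a minor correction. The analyte is misnamed in all four cells of the creatinine row. On the literal text CK grades differ by one level over three ranges (baseline at ULN assumed), and creatinine is ungraded or Grade 0. The reach is one summary of maximum grade and the grade-based part of one listing. This takes the maximum-grade summary to cover all gradable tests, since SAP 5.7.3.1 attaches its list of named parameters to the shift tables.

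The haemoglobin item is secondary. The SI figure is about 16 times the stated g/dL limit on the SAP's own conversion, but the effect is ambiguity within one criterion and not blocked enrolment.

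The primary endpoint, sample size, alpha and proof-of-concept decision are untouched by either item.

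**What to change.** In SAP Appendix 10, replace creatine kinase with creatinine in the four grade cells of the *Creatinine increased* row so that they match its label, and grade CK in the CPK row only. Check that the grading program applies each row to the analyte in its label before the graded tables are produced.

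In protocol criterion 12.1a, reconcile the SI entry with the stated 9 g/dL; the number 90 fits only if the unit is g/L.

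The cost is one table row in the SAP and one unit in a protocol amendment, with no new data and no change to any efficacy analysis.

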6.11. Appendix 11 A Prohibited Change in SSC Medication

- New start of prohibited and restricted therapies during the study which are defined in the protocol Section 6.8:
 - IL-23 inhibitor therapy (including but not limited to guselkumab, risankizumab, tildrakizumab, brazikumab, mirikizumab)
 - tocilizumab
 - sirukumab, sarilumab, mavrilimumab, abatacept, belimumab
 - IL-12/23 inhibitors (ustekinumab)
 - IL-17 inhibitors (secukinumab, ixekizumab, brodalumab)
 - tyrosine kinase inhibitor (nintedanib)
 - Any live viral or live bacterial vaccination
 - Rituximab
 - Any cytotoxic agents (cyclophosphamide, chlorambucil, nitrogen mustard, or other alkylating agents)
 - Intravenous immunoglobulin (IVIG), apheresis therapy (plasmapheresis or leukapheresis)
 - Systemic immunosuppressive agents (including but not limited to cyclosporine A, azathioprine, tacrolimus, sirolimus, methotrexate, sulfasalazine, leflunomide with cholestyramine washout or mycophenolate mofetil/mycophenolic acid)
 - Intramuscular, intra-articular, intrabursal, epidural, intralesional or IV GCs
 - Pirfenidone
 - Systemic and topical Janus kinase inhibitors (eg, tofacitinib, upadacitinib)
 - Other biologics
 - Any investigational agents/treatments
- Treat with rescue therapy before Week 24, including:
 - 1) Oral Corticosteroid \leq 20 mg/day of prednisolone or equivalent
 - 2) Immunomodulator (Azathioprine), within the approved dose for SSc
- New start of oral Corticosteroid (prednisolone or equivalent) before Week 24.
- Significant increase of oral Corticosteroid (prednisolone or equivalent) before Week 24.

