5.3.2. Estimands

1. Primary Estimand (Composite Estimand)

The primary estimand is defined as the following components:

Primary Trial Objective: to evaluate the efficacy of guselkumab in participants with SSc

Estimand Scientific Question of Interest: what is the efficacy, as is measured by change from baseline in mRSS at Week 24 for participants who are assigned to guselkumab versus placebo

Study Intervention:

- Experimental: guselkumab
- Control: placebo

Population: participants between 18 to 75 years (inclusive) with diagnosis of SSc according to ACR and EULAR 2013 criteria with a disease duration of ≤ 36 months (defined as time from first non-Raynaud phenomenon manifestation), and mRSS ≥ 10 to ≤ 22 units

Variable: change from baseline in mRSS at Week 24. Participants with an intercurrent event before Week 24 will have a zero change from baseline in the mRSS since the intercurrent event occurs, regardless of the observed data.

Summary measure (Population-level summary): difference in least-square means (LSMs) of change from baseline in mRSS at Week 24 between guselkumab vs placebo

Intercurrent events and their corresponding strategies:

Intercurrent Events	Strategy for Addressing Intercurrent Events and Its Description
A prohibited change in SSc medication (for details, see Appendix 11)	Composite Strategy: A participant with this intercurrent event is considered to have a zero change at and after the event occurred.
Discontinuation of study intervention due to lack of efficacy or an AE of Systemic Sclerosis	Composite Strategy: Same as above

2. Supplementary Estimand (Hypothetical Estimand)

This supplementary estimand will be used to complement the primary estimand. The components of the supplementary estimand are the same as those for the primary estimand with the exception of definitions in Variable and Intercurrent event strategies (**hypothetical strategy**), which are described as follows:

Variable: change from baseline in mRSS at Week 24. Participants with an intercurrent event before Week 24 will have their mRSS set to missing since the intercurrent event occurs.

Intercurrent events and their corresponding strategies:

Intercurrent Events	Strategy for Addressing Intercurrent Events and Its Description
A prohibited change in SSc medication (for details, see Appendix 11)	Hypothetical Strategy: A participant with this intercurrent event is considered to have missing data at and after the event occurred.

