Change from baseline in digital ulcer counts at Week 24	Difference in LSMs of change from baseline in digital ulcer counts at Week 24 between guselkumab vs placebo
Change from baseline in digital ulcer counts at Week 52	Difference in LSMs of change from baseline in digital ulcer counts at Week 52 between guselkumab vs placebo
Change from baseline in HAQ-DI score at Week 24	Difference in LSMs of change from baseline in HAQ-DI score at Week 24 between guselkumab vs placebo
Change from baseline in HAQ-DI score at Week 52	Difference in LSMs of change from baseline in HAQ-DI score at Week 52 between guselkumab vs placebo

Intercurrent events and their corresponding strategies:

The intercurrent events for all key secondary endpoints at Week 24 are the same as those in the primary estimand, as follows:

1. A prohibited change in SSc medication (for details, see [Appendix 11](#))
2. Discontinuation of study intervention due to lack of efficacy or an AE of Systemic Sclerosis

As rescue medication is available for participants after Week 24, an additional intercurrent event is defined for secondary efficacy endpoints at Week 52.

3. Initiation of rescue medication after Week 24

Intercurrent events 1, 2 and 3 are all handled by the **composite strategy** to assume that the occurrence of intercurrent events indicates an unfavorable outcome. For continuous endpoints, the change from baseline will be zero; and for binary endpoints, the participants are considered as not achieving an improvement (ACR CRISS score ≥ 0.6) or experiencing worsening (an increase from baseline ≥ 5 points and $\geq 20\%$ in mRSS).

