As to time to event endpoint, ie, time to disease worsening, it will be summarized by Kaplan-Meier method, with the median, 25th, and 75th percentiles and 95% CI for the quartiles. The comparison between guselkumab and placebo will use a Cox proportional hazards model adjusting for the stratification factors at randomization. An 80% CI for the hazard ratio (HR) will be produced. The

same intercurrent events and handling strategy defined in Section [5.4.2.2](#) will be applied to this endpoint as well, the detailed definition of censoring and event is described as below:

No.	Situation	Date of Event or Censoring	Outcome
1	Disease worsening: an increase from baseline ≥ 5 and $\geq 20\%$ in mRSS or decrease $>10\%$ from baseline in FVC %	First occurrence of disease worsening	Event
2	A prohibited change in SSc medication on or before Week 52	First occurrence of prohibited change	Event
3	Discontinuation of study intervention due to lack of efficacy or an AE of SSc before Week 52	Date of discontinuation of study intervention	Event
4	Initiation of rescue medication after Week 24 and through Week 52	Date of initiation of rescue medication	Event
5	Other	Date of last mRSS or FVC assessment through Week 52	Censored

Note: if participants had more than one items of 1,2,3,4 occurred, the date of first occurrence will be considered as event date.

Unless otherwise specified, LTE efficacy endpoints will only be summarized using descriptive statistics.

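### SAP Appendix 11 counts a live vaccination as a prohibited SSc medication change, so a vaccinated participant is scored as an efficacy failure for a reason unrelated to the disease

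*SAP*

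**What the plan says.** **Event definition.** SAP Appendix 11 opens with "New start of prohibited and restricted therapies during the study which are defined in the protocol Section 6.8" and then repeats the protocol's list item by item. One item is "Any live viral or live bacterial vaccination". Nothing in the appendix limits the event to changes made for SSc, and no section exempts vaccination.

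**Primary estimand (SAP 5.3.2).** The first intercurrent event refers to Appendix 11 for its content. The handling is composite: "A participant with this intercurrent event is considered to have a zero change at and after the event occurred". The variable definition adds that participants with an event before Week 24 "will have a zero change from baseline in the mRSS since the intercurrent event occurs, regardless of the observed data".

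**Secondary estimands (SAP 5.4.2.2).** "The intercurrent events for all key secondary endpoints at Week 24 are the same as those in the primary estimand", and initiation of rescue medication is added for Week 52. Continuous changes become zero. Binary endpoints are scored as no ACR CRISS improvement or as mRSS worsening. The stated reason is to "assume that the occurrence of intercurrent events indicates an unfavorable outcome".

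**Exploratory endpoints (SAP 5.5.2).** The same events and strategy apply to FVC decline and FVC worsening through Week 52. In the time-to-disease-worsening table, "A prohibited change in SSc medication on or before Week 52" is an event dated at its first occurrence.

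**Protocol.** Section 2.3.1 places the live-vaccine restriction among the measures against infection risk. Section 6.8 includes it in the general list of prohibited and restricted therapies.

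**The concern.** A composite strategy is justified when the event itself is evidence about the outcome. Starting rituximab or cyclophosphamide can fairly be read as a sign that the disease was not controlled. A live vaccination carries no such information, and neither document gives a reason to think it does. The item fits neither the title of the appendix nor the rationale in SAP 5.4.2.2.

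The second intercurrent event is narrower: it covers discontinuation only for lack of efficacy or an AE of systemic sclerosis. Stopping treatment for an unrelated AE is therefore not scored as failure, whereas one vaccine dose is. At stake is the overwriting of valid mRSS, FVC, DLCO, digital ulcer, HAQ-DI and ACR CRISS data for a reason unrelated to SSc.

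**Working it through.** **1. Plan's own figure.** Inputs from SAP Section 3: SD 8, difference 4.7, two-sided alpha 0.20, power 80%, 1:1 allocation.

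n per arm = 2 × [8 × (1.2816 + 0.8416) / 4.7]² = 26.12, rounded up to 27. That gives 54 in total, and 56 with the allowance of 2. The stated size reproduces and does not depend on the vaccination item.

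**2. Tracing one live vaccination through the SAP.**

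| Endpoint | Section | Score imposed | Exposed period |
|---|---|---|---|
| mRSS change, Week 24 (primary) | 5.3.2 | 0 | before Week 24 |
| mRSS, FVC, DLCO, digital ulcer and HAQ-DI change (secondary) | 5.4.2.2 | 0 | to Week 24 or Week 52, by endpoint |
| ACR CRISS ≥ 0.6 | 5.4.2.2 | not improved | same |
| mRSS worsening | 5.4.2.2 | worsened | same |
| FVC decline, FVC worsening | 5.5.2 | declined, worsened | through Week 52 |
| Time to disease worsening | 5.5.2 | event | on or before Week 52 |

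**3. Shift in an arm mean from one case (28 per arm).** Shift = observed change / 28.
- Observed -5: 5/28 = 0.18 points
- Observed -10: 10/28 = 0.36 points

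The -5 to -10 range is an assumption. The figures are for the simple mean; the MMRM estimate would move by a similar but not identical amount.

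**4. Size against the noise.** SE of the difference = 8 × √(2/28) = 2.14 points. 0.18/2.14 = 8% and 0.36/2.14 = 17%.

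**5. Direction.** Zero overrides worsening as well as improvement. A participant observed at +5 would be scored 5 points better. The arm matters too: zeroing an improver on placebo widens the difference in favour of guselkumab. The sign is therefore not fixed.

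**6. Binary endpoints.** One participant is 1/28 = 3.6 percentage points of an arm. A false worsening event arises only if the participant had not in fact worsened. A false CRISS non-response arises only if the participant would otherwise have responded. From the equation in SAP 5.4.2.1, with the other four components unchanged and no Step 1 condition:
- mRSS change -5: -5.54 + 0.81 × 5 = -1.49; exp(-1.49) / [1 + exp(-1.49)] = 0.18, already a non-responder
- Probability 0.60 requires (0.405 + 5.54) / 0.81 = 7.3 points of mRSS improvement

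**7. Power, for illustration.** Assume k of 28 guselkumab participants are vaccinated before Week 24 and none on placebo, with true difference -4.7, SD 8 and placebo mean change between 0 and -4. Normal-approximation power with 28 per arm is 82.0% at k = 0. At k = 1 the expected difference is -4.53 to -4.39 and power is 79.9% to 78.0%. The documents give neither k nor the placebo change.

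**8. Other planned analyses.** For Week 24 mRSS, Supplementary Analysis 1 sets post-event values to missing and Supplementary Analysis 2 keeps them as observed. The Week 52 mRSS supplementary analysis (SAP 5.4.2.4) relaxes only rescue medication. No comparable analysis is given for ACR CRISS, mRSS worsening, FVC or time to worsening.

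**The case against.** **It may never happen.** Live vaccination is prohibited during the study, and recent live vaccination is an exclusion criterion (Protocol 5.2, 6.8). The documents are compatible with no cases, in which case no result changes. This stands and limits the size of the point. It does not make the rule right when triggered.

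**The primary endpoint is already covered.** Supplementary Analyses 1 and 2 would show any effect on Week 24 mRSS. This stands for that endpoint only; the primary analysis still carries the p < 0.2 decision.

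**Observed data may not exist.** Protocol 7.1 requires study intervention to stop when a prohibited therapy starts, unless agreed with the medical monitor, and later visits may be missing. This stands, so the fix must say how missing data are handled. Such a stop would not by itself meet the second intercurrent event; the failure score comes from the Appendix 11 listing.

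**Copying the protocol list is objective, and other items may also be given for non-SSc reasons.** Intra-articular glucocorticoids are an example. The point about objectivity is fair, but a named exception for live vaccines is equally objective. Glucocorticoids can at least be argued to affect the disease measures.

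**Stronger readings the documents do not support.** A reader might infer that the rule biases the trial against guselkumab, that every vaccination adds a false CRISS non-responder, or that power falls below 80%. Steps 5 and 6 rule out the first two as general statements. The third depends on an assumed case count, confined to one arm, that the documents do not give.

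**Conclusion.** The definition is too broad as written and conflicts with the SAP's own reason for the composite strategy. The primary endpoint is exposed only to vaccinations before Week 24; the Week 52 and time-to-event endpoints are exposed through Week 52.

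The expected impact is small. Per case, and assuming an observed change of -5 to -10, an arm mean moves 0.18 to 0.36 points, or 8% to 17% of the planning SE (SD 8, 28 per arm). An arm's worsening rate can rise by 3.6 percentage points if the participant had not worsened, and its non-response rate by the same amount if the participant would have responded. The number of cases is unknown and may be zero. It would be wrong to infer that the proof-of-concept decision is in jeopardy. The case for acting is that the rule gives a wrong score whenever it is triggered, that most affected endpoints have no analysis that would reveal it, and that the correction is very cheap.

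**What to change.** Before database lock:

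- Delete the live-vaccination line from SAP Appendix 11.
- Add an explicit exception for live viral and live bacterial vaccines to the lead-in that cites Protocol 6.8. Deleting the line alone is not enough, because the lead-in would still bring in the whole protocol list.
- State that live vaccination is handled by treatment policy for all efficacy endpoints: data observed after it are used, and data missing after any resulting discontinuation follow the MAR approach in SAP 5.1.2.
- Continue to report it as a protocol deviation under SAP Appendix 4 (disallowed concomitant treatment).

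The cost is a few lines of SAP text and a matching change to the event-flag programming. It needs no new data and no change to the sample size or to the protocol's prohibition. It should be made while treatment assignments are still blinded, because removing an event definition after unblinding would look data-driven.
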